## 9.4.3.2. Patients with History of Cardiac Disease

In Part A of the study, patients with any clinically relevant cardiovascular conditions, as listed out in the exclusion criteria (Section 9.4.2), are excluded from participating in the study.

In Part B, patients with some pre-existing cardiac conditions, who have stable disease and would not be placed at significant safety risk by participating in the study, may be considered for participation in Part B of the study. Please refer to Section 9.4.2 for a list of cardiac exclusion criteria for Part B. These patients should have a cardiology consultation to determine whether it is appropriate for them to participate in Part B of the study and whether they need additional

cardiac monitoring, such as being monitored for an extended period of time and/or possible extended continuous ECG monitoring overnight in a medical facility.

If more intensive monitoring is not deemed necessary by the consulting cardiologist, these patients will follow the detailed first dose monitoring procedures as outlined in Section10.2.1.1. The treating investigator should ensure these patients included in the study are closely monitored for signs of any bradycardia or other rhythm disturbances after the first dose of RPC1063, as these patients may be at higher risk for cardiac adverse events.

## 9.4.4. Withdrawal of Patients from Study Medication and/or the Study

## 9.4.4.1. Discontinuation of Study Medication

Reasons for discontinuation include, but are not limited to the following:

#### Investigator decision

The Treating Investigator may discontinue study medication if it is determined that it is not safe or in the patient's best interest to receive further treatment. The Medical Monitor should be promptly notified of the decision.

- Noncompliance: after consultation between the investigator, the Medical Monitor, or Study Monitor, and the sponsor when appropriate, a patient may be discontinued from study medication for failure to comply with protocol requirements
- Intercurrent illness: A patient may be discontinued from study medication if, in the judgment of the treating investigator, the patient develops an intercurrent illness or complication that is not consistent with the protocol requirements or that, in any way, justifies discontinuation of study medication.
- Protocol-defined adverse events of special interest (see Section 12.4):
  - Confirmed AST or ALT >5 times the upper limit of the normal range, confirmed upon retest within 14 days of the original lab value (unless determined by the investigator to not be of hepatic origin)
  - o A diagnosis of macular edema, which is new or worsening since baseline
  - o FEV1 or FVC <50% of predicted values
- If the patient becomes pregnant
- Sponsor termination or suspension of the study

All patients who discontinue study medication should complete an Early Termination Visit (see Table 2 [Part A] and Table 4 [Part B]). Unless the patient withdraws consent or is lost to follow-up, they will be asked to undergo a follow-up visit 4 weeks after the last dose for the collection of safety data including lymphocyte recovery and to assess their disease status. Alternative treatment for multiple sclerosis (with the exception of medication given in the context of another clinical trial) can be started, if needed, after the early termination visit.

The reason for discontinuation of study medication will be recorded in the clinical records and the patient's eCRF.

## 9.4.4.2. Withdrawal of Patients From the Study

Patients must be withdrawn from the study for any one of the following reasons:

- The patient is lost to follow up (i.e., those patients whose status is unclear because they fail to appear for study visits without stating an intention to withdraw), the investigator should show due diligence by documenting in the source documents steps taken to contact the patient (e.g., dates of telephone calls, registered letters).
- Patient withdrawal of consent. Every effort should be made within the bounds of safety and patient choice to have each patient complete the study. If a patient withdraws consent, the only additional study data to be collected will be the follow up of SAEs as mandated by the protocol.

The reason for the patient's withdrawal from the study must be recorded in the clinical records and the patient's eCRF.

#### 9.5. Treatment

#### 9.5.1. Treatments Administered

The Investigator must ensure that the investigational product will be used only in accordance with the protocol.

Part A of the study is randomized and double-blinded with regard to treatment with RPC1063 and matching placebo in order to prevent bias in treatment allocation and in the assessment of effect. The Investigator site personnel, as well as the Sponsor and their representatives involved in the monitoring or conducting the study, and the patients will all be blinded to the study drug codes.

Part B of the study is randomized and double-blind, double-dummy with regards to treatment with RPC1063 or IFN  $\beta$ -1a and their corresponding matching placebo in order to prevent bias in treatment allocation and in the assessment of effect. The prolonged treatment period (24 months) will provide additional safety and efficacy data; information that is relevant to RMS, a chronic, highly variable, slowly progressing disease.

In both Part A and Part B of the study, a "dual assessor" approach will be used to evaluate efficacy and safety to prevent potential unblinding as result of observed efficacy, AEs, or laboratory changes

#### Part A

In Part A, patients will be randomly assigned 1:1:1 on Day 1 to one of following 3 treatment regimens:

- Placebo oral capsule daily for 24 weeks
- 0.5 mg RPC1063 oral capsule daily for 24 weeks
- 1 mg RPC1063 oral capsule daily for 24 weeks

For all patients in Part A, initial study treatment will consist of a 7-day dose titration regimen as follows (see Table 6): for patients randomized to receive active treatment with RPC1063, this regimen will consist of 0.25 mg RPC1063 starting on Day 1 for 4 days and 0.5 mg RPC1063

starting on Day 5 for 3 days. All patients will be dosed with their assigned treatment level beginning on Day 8.

Table 6 Titration Schedule for the RPC1063 Treatment Groups in Part A

	RPC1063/Placebo dose (# capsules)						
Assigned treatment	Days 1 to 4	Days 5 to 7	From Day 8 on				
RPC1063 0.5 mg	0.25 mg	0.5 mg	0.5 mg				
	(1 x 0.25 mg capsule)	(2 x 0.25 mg capsules)	(1 x 0.5 mg capsule)				
RPC1063 1 mg	0.25 mg	0.5 mg	1 mg				
	(1 x 0.25 mg capsule)	(2 x 0.25 mg capsules)	(1 x 1 mg capsule)				
Placebo	Placebo	Placebo	Placebo				
	(1 capsule)	(2 capsules)	(1 capsule)				

Study medication will begin following randomization (Section 13.4) on Day 1. Patients will take capsule(s) daily through Week 24.

Capsule dosing: dosing will be once daily in the morning in fasting conditions (before breakfast).

On days of study visits on which a pre-dose PK sample will be obtained (Day 1 and Week 12 in Part A, Day 1 and Month 12 in Part B), patients should be instructed to withhold the dose and their morning meal until the office visit, and dose will be administered during the visit.

#### Part A Blinded Extension Period

In the blinded extension period of Part A, patients will receive 1 of the 2 following treatment regimens:

- 0.5 mg RPC1063 oral capsule daily beginning on Week 25
- 1 mg RPC1063 oral capsule daily beginning on Week 25

RPC1063 0.5 mg or 1 mg patients who have completed the 24-week placebo-controlled treatment period and who choose to participate in the blinded extension period will continue in their respective treatment groups.

Placebo patients who have completed the 24-week placebo-controlled treatment period and who choose to participate in the blinded extension period will be randomized 1:1 to either the 0.5 mg or 1 mg RPC1063 treatment regimen.

All patients who participate in the optional blinded extension period will have an initial 7-day dose titration period as shown in Table 6: 0.25 mg RPC1063 starting on Day 1 for 4 days and 0.5 mg RPC1063 starting on Day 5 for 3 days. Day 1 cardiac monitoring procedures will also be performed on the first day of dose titration, as shown in Table 5. (Holter monitoring will not be included in these cardiac monitoring procedures.) Patients will be dosed with their assigned treatment level beginning on Day 8.

Patients who opt to enter the optional, blinded extension period will continue to receive study drug until all patients who choose to participate have received at least 48 weeks of treatment (total of at least 72 weeks, 24 weeks in the placebo-controlled period and at least 48 weeks in the blinded extension).

Treatment in case of relapse is described in Section 9.1.2.3.

#### Part B

In Part B, patients will be randomized 1:1:1 to receive one of the following 3 regimens:

- IFN β-1a 30 µg IM injection weekly for 24 months
- 0.5 mg RPC1063 oral capsule daily for 24 months
- 1 mg RPC1063 oral capsule daily for 24 months

Dosing will begin following randomization on Day 1.

Part B will be use a double-dummy design. Thus, patients randomized to RPC1063 0.5 or 1 mg will also receive weekly matching placebo IM injections and patients randomized to IFN  $\beta$ -1a 30  $\mu$ g will also receive daily matching placebo oral capsules.

For all patients in Part B, initial study treatment will consist of a 7-day dose titration regimen as shown in Table 7: for patients randomized to receive treatment with RPC1063, this regimen will consist of 0.25 mg RPC1063 starting on Day 1 for 4 days, and 0.5 mg RPC1063 starting on Day 5 for 3 days. All patients will be dosed with their assigned RPC1063 treatment level beginning on Day 8. Patients randomized to IFN  $\beta$ -1a 30  $\mu$ g will receive RPC1063-matching placebo titration kits.

Table 7 Titration Schedule for the RPC1063 Treatment Groups in Part B

	RPC1063/IFN β-1a dose (# RPC1063/Placebo capsules)							
Assigned treatment	Day 1	Days 2 to 4	Days 5 to 7	Day 8*				
RPC1063 0.5 mg	0.25 mg RPC1063 (1 x 0.25 mg capsule) + Placebo	0.25 mg RPC1063 (1 x 0.25 mg capsule)	0.5 mg RPC1063 (2 x 0.25 mg capsules)	0.5 mg RPC1063 (1 x 0.5 capsule) + Placebo IM injection				
RPC1063 1 mg	IM injection  0.25 mg RPC1063  (1 x 0.25 mg  capsule)  +  Placebo  IM injection	0.25 mg RPC1063 (1 x 0.25 mg capsule)	0.5 mg RPC1063 (2 x 0.25 mg capsules)	1 mg RPC1063 (1 x 1 mg capsule) + Placebo IM injection				
IFN β-1a 30 μg	IFN β-1a 30 μg- IM injection + Placebo (1 capsule)	Placebo (1 capsule)	Placebo (2 capsules)	IFN β-1a 30 μg- IM injection + Placebo (1 capsule)				

\* From Day 8 on, patients will continue receiving weekly IM injections (IFN β-1a/ placebo) and daily capsules (RPC1063/placebo) according to the assigned treatment level

IFN  $\beta$ -1a 30  $\mu g$  (and matching placebo) will be supplied in sealed plastic trays containing one prefilled syringe for IM injection for each dosing interval. Patients will be instructed by a nurse or physician how to self-administer injections. The first injection will be self-administered under the supervision of a nurse or physician. Thereafter, patients will self-administer their study treatment (IFN  $\beta$ -1a or matching placebo) once weekly. Further instructions on how patients

Efficacy and Safety of Oral RPC1063 in RMS Patients

01 October 2014 Version 4.0

should self-inject are provided in the study injection guide (information for the user) that will be provided to the patients.

RPC1063 and matching placebo capsules will be taken in fasting conditions as described above in Part A.

Treatment in case of relapse is described in Section 9.1.2.3.

On the days of IFN  $\beta$ -1a/placebo IM injection administration, prophylactic treatment of flu-like symptoms is recommended as follows:

Acetaminophen (paracetamol) or ibuprofen within 1 hour prior to each IFN β-1a injection, and then approximately every 6 hours for the 24 hours following each injection.

If the patient cannot take either acetaminophen (paracetamol) or ibuprofen, then the patient may take:

• Naproxen within 1 hour prior to IFN β-1a injection, and then approximately every 12 hours for the 24 hours following each injection.

If the patient cannot take acetaminophen (paracetamol), ibuprofen, or naproxen, then:

• Aspirin may be administered within 1 hour prior to each IFN β-1a injection and then approximately every 4 to 6 hours for the 24 hours following each injection.

Patients may take additional doses of acetaminophen (paracetamol), ibuprofen, naproxen, or aspirin within a 24-hour period as necessary for the relief of IFN-related flu-like symptoms.

Patients should be told to refer to the medication label/packaging for the recommended individual and maximum total doses within any 24-hour period.

#### Instructions for Missed Dose(s) of RPC1063/Placebo Capsules

Patients should be instructed that if they forget to take a dose, they can take the dose within 4 hours of the normal dosing time; otherwise they should take their next dose at the regular time on the following day. If the patient vomits the capsule, he/she should be instructed not to take another capsule on the same day, but to take the next dose at the regular time on the following day. If the patient is ill and unable to take a dose, 2 days without treatment is acceptable, otherwise the patient will contact the Investigator.

If a patient misses a dose during dose titration, the Medical Monitor should be contacted to discuss completing the dose titration schedule.

If the patient misses more than 7 consecutive doses for any reason, Day 1 cardiac monitoring procedures will be performed on the first day that the patient resumes dosing (Holter monitoring will not be performed). If a patient misses more than 14 consecutive doses for any reason, the Medical Monitor must be contacted to discuss procedures for resuming therapy, which may include an additional dose titration schedule if deemed appropriate.

#### Instructions for Missed Dose of IFN β-1a/Placebo Injection

Patients should be instructed that if they forget to take a dose, they can administer the injection within 2 days of the scheduled weekly dosing day. Prophylactic treatment should be administered prior to injection as described above. If the patient does not administer the

injection within 2 days of the scheduled injection day, they should take their next dose on the next scheduled weekly injection day.

#### 9.5.2. Study Treatment Formulation

## **RPC1063 Capsules and Placebo**

The drug substance will be manufactured, quality control checked and released in accordance with good manufacturing practices at supply the study medication (RPC1063 capsules and matching placebo).

RPC1063 and placebo will be provided as powder-filled capsules. RPC1063 drug substance is blended with

capsules. Three RPC1063 dosage strengths have been prepared for the clinical investigations; 0.25 mg ( capsule), 0.50 mg ( capsule), and 1.0 mg ( capsule).

For placebo, the same capsules

will contain the same blended excipients described above. All three doses of RPC1063 and placebo capsules are identical in appearance.

The capsules will be orally administered singularly, or in varying combinations, to achieve the desired dose for clinical studies.

## IFN β-1a and Matching Placebo

IFN  $\beta$ -1a is commercially available and is manufactured by . Stocks of

IFN  $\beta$ -1a will be purchased directly from the supplier and supplied by

IFN  $\beta$ -1a matching placebo will be manufactured, quality control checked and released in accordance with good manufacturing practices at

IFN  $\beta$ -1a matching placebo for injection will contain 0.9% Sodium Chloride.

Study treatment IFN  $\beta$ -1a and matching placebo will be supplied in prefilled syringes, which will be dispensed to patients at each visit and will contain a sufficient supply of IFN  $\beta$ -1a 30  $\mu$ g/0.5 mL for IM injection at each dosing interval.

Study treatment (IFN  $\beta$ -1a or matching placebo) prefilled syringes and needles are for one-time use only; any study treatment remaining should not be used for another dose.

All study medication must only be dispensed by a Pharmacist or medically qualified staff and is to be dispensed only to patients enrolled in this study.

# 9.5.3. Study Treatment Labeling and Packaging

RPC1063 capsules will be packaged in

(35 capsules per bottle, apart from the titration kits), closed with a child resistant screw-cap that is induction sealed.

The labeling will be in accordance with GCP and any other local regulatory requirements.

Details unique to Parts A and B are described below.

#### Part A

Similar to RPC1063 capsules, placebo capsules will be packaged in

(35 capsules per bottle for treatment medication capsules, and 12 capsules per bottle in the titration kits), closed with a child resistant screw-cap that is induction sealed. The cap on the treatment bottles will be white, and the cap on the titration bottles will be blue.

The labeling will be in accordance with GCP and any other local regulatory requirements.

## Part B

IFN  $\beta$ -1a and matching placebo injections will be supplied in prefilled syringes, which will be dispensed to patients at each visit and will contain a sufficient supply of IFN  $\beta$ -1a (or matching placebo) for each dosing interval. Treatment kits must be stored in a secure location. Accountability for study treatment is the responsibility of the Investigator. More details concerning this responsibility are included in Section 9.5.5.

## 9.5.4. Blinding of Study Medication

In Parts A and B, a "Dual Assessor" approach (described in Section 9.1.2.2) will be used to evaluate efficacy and safety.

Details unique to Parts A or B are described below.

#### Part A

Part A is a randomized, double-blind, placebo-controlled study with limited access to the randomization code. RPC1063 and placebo capsules will be identical in physical appearance. The treatment each patient will receive will not be disclosed to the Investigator, Evaluator, study center personnel, patient, Sponsor and their representatives. The treatment codes will be held according to an IVRS. Further instructions will be provided in a separate IVRS manual.

#### Part B

Part B is a randomized, double-blind, double-dummy, active-controlled study. RPC1063 and IFN  $\beta$ -1a and their respective matching placebo capsules/injections will be identical in physical appearance. The treatment each patient will receive will not be disclosed to the Investigator, Evaluator, study center personnel, patient, Sponsor and their representatives. The treatment codes will be held according to an IVRS. Further instructions will be provided in a separate IVRS manual.

For details of the emergency procedure for unblinding of individual patients see Section 9.5.11, below.

## 9.5.5. Study Treatment Storage and Accountability

Study medication should not be used for purposes other than as defined in this protocol.

# 9.5.5.1. Study Treatment Storage

#### Part A

RPC1063 and placebo capsules should be stored at room temperature (approximately 25° C, excursions permitted to 15-30°C [59-86°F]) in a dry location. The inactive ingredients used in

the formulations are slightly hygroscopic; therefore, all bottles contain a ½-gram desiccant canister and should be kept tightly sealed when drug product is not being dispensed.

#### Part B

IFN  $\beta$ -1a prefilled syringes (and matching placebo) must be stored in a secure location. They must be stored at 2-8°C.

RPC1063 capsules will be stored as described for study medication capsules in Part A.

## 9.5.5.2. Study Treatment Accountability

All supplies of study medication and placebo will be accounted for in accordance with GCP. There will be an individual study drug accountability record for each patient and the Investigator should maintain accurate records of the disposition of all study medication supplies received during the study. These records should include the amounts and dates clinical drug supplies were received, dispensed to the patient, returned by the patient and returned to the Sponsor. If errors or damages in the clinical drug supply shipments occur, the Investigator should contact and the Study Monitor immediately. Each Investigator will provide copies of the study medication accountability records for inclusion in the Trial Master File after database lock. The Study Monitor will periodically check the supplies of study medication held by the Investigator or pharmacist to verify accountability of all medication used.

The Investigator will provide the medication only to the identified patients of this study, according to the procedures described in this study protocol. After the end of the study, the Study Monitor will perform final accountability, package, seal, and prepare for shipment. Medication and all medication containers will be returned to and documentation will be returned to the CRO. The CRO will verify that a final report of drug accountability is prepared and maintained in the Investigator's Study Center File.

#### 9.5.6. Dose Adjustments and Dose Escalation

There is no provision for dose adjustments in this study. Patients who cannot tolerate investigational drug must be withdrawn from the study

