#### Part A and Part B

Study assessments will include physical examination, vital signs, blood tests and MRI (without and with Gadolinium contrast). Several of the AEs noted in fingolimod clinical studies may be a consequence of S1P1R stimulation and will therefore be closely monitored in the study. These AEs include bradycardia and heart conduction abnormalities (electrocardiogram [ECG] monitoring, Holter monitoring [Part A only], vital signs), pulmonary toxicity (forced expiratory volume at 1 second [FEV1], forced vital capacity (FVC) measurements, and lung diffusion capacity testing [DLCO] measurements), macular edema (ophthalmic monitoring including optical coherence tomography [OCT]), cutaneous malignancy (dermatological exams) and hepatotoxicity (liver function tests [LFTs]).

Patients who experience a relapse may receive treatment with intravenous (IV) corticosteroids. The following standardized treatment regimen should be used: as warranted, 1.0 g IV methylprednisolone per day for a maximum of 5 consecutive days. A corticosteroid taper is not allowed. Any deviation from the standardized treatment regimen should be discussed in advance with the Medical Monitor. The Investigator should attempt to maintain therapies or treatments for symptoms related to MS (e.g., spasticity, incontinence, pain, fatigue) reasonably constant throughout the study. However, changes may be made if appropriate for a patient's well-being in the clinical judgment of the treating investigator.

All efforts will be made to follow patients who discontinue prematurely from the treatment due to lack of response, AEs, or other reasons, even if alternative treatment is given. These patients will be followed for collection of safety data, including lymphocyte recovery, and for the assessment of their disease status. The Cognitive Function subscale of the MSQOL-54 will be assessed to evaluate quality of life and subjective cognitive impairment.

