# Part B

Part B is a randomized, double-blind, double-dummy comparison of RPC1063 to IFN  $\beta$ -1a in patients with RMS, per revised 2010 McDonald criteria (McDonald, 2010; Polman, 2011). Part B will commence after the DMC reviews the Part A interim analysis data and performs a thorough safety review. Patients dosed in Part A will be ineligible for participation in Part B.

Approximately 1200 patients who meet eligibility criteria as assessed during the 30-day screening period will be randomly assigned 1:1:1 to receive one of the three following regimens for 24 months:

- IFN β-1a 30 µg intramuscular (IM) weekly
- 0.5 mg RPC1063 oral capsule daily
- 1 mg RPC1063 oral capsule daily

The randomization will be stratified by baseline EDSS ( $\leq 3.5, > 3.5$ ) and country.

A "dual assessor" approach will be used to evaluate efficacy and safety to prevent potential unblinding as result of observed efficacy, AEs, or laboratory changes (refer to Section 9.1.2.1 for additional details). The treating investigator will evaluate patients every 3 months throughout the study and, if necessary, at unscheduled visits for relapses occurring between scheduled visits.

[figure not shown]
The blinded evaluator will assess the EDSS. Blinded study coordinators or EDSS evaluators will perform the MSFC and LCLA assessments. The Cognitive Function subscale of the

MSQOL-54 will also be assessed to evaluate subjective cognitive impairment. The Paced Auditory Serial Addition Test (PASAT-3) of the MSFC will also be used to evaluate cognitive function.

All efforts will be made to follow patients who discontinue from the treatment due to lack of response, AEs, or other reasons, even if alternative treatment is given. These patients will be followed for collection of safety data, including lymphocyte recovery, and for the assessment of their disease status.

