#### Part A

At each visit, previously dispensed study medication capsules will be collected by the Investigator and compliance assessed. Patients will record capsules intake in a dosing diary that will be reviewed periodically by site staff and the Clinical Monitor. Patients exhibiting poor compliance as assessed by medication counts (i.e., 2 or more missed medication days in 1 week) and response to the question "Did you take your medication regularly?" should be counseled on the importance of good compliance to the study dosing regimen. Patients who are persistently non-compliant (< 80% or > 120%) should be discussed with the Medical Monitor to determine whether they should be withdrawn from the study.

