#### Part B

Compliance with IFN  $\beta$ -1a dosing is to be monitored and recorded by site staff. Patients will record IFN  $\beta$ -1a treatment in a dosing diary that will be reviewed periodically by site staff and the Clinical Monitor.

Compliance with RPC1063 capsules will be assessed as described above for Part A.

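### Section 9.5.6 removes patients who cannot tolerate the drug from the study, against the follow-up after stopping treatment promised in the synopsis and Section 9.1

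*Protocol*

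**What the plan says.** Section 9.5.6 of the protocol (Dose Adjustments and Dose Escalation) rules out dose adjustment and then says: "Patients who cannot tolerate investigational drug must be withdrawn from the study". It applies to both parts of the study and gives no exception.

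Other sections treat the same patient differently:

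- **Synopsis, Part A and Part B:** "All efforts will be made to follow patients who discontinue prematurely from the treatment due to lack of response, AEs, or other reasons". This holds even if other treatment is given, and the follow-up covers safety and disease status.
- **Section 9.1, Part B:** "All efforts will be made to follow patients who discontinue from the treatment due to lack of response, AEs, or other reasons", for the same two purposes.
- **Section 9.4.4.1 (Discontinuation of Study Medication):** confirmed liver enzymes above 5 times the upper limit, new or worse macular edema, and FEV1 or FVC below 50% of predicted are reasons to stop study medication. The patient then has an Early Termination visit and, unless lost or consent is withdrawn, a visit 4 weeks after the last dose "for the collection of safety data including lymphocyte recovery and to assess their disease status".
- **Section 9.4.4.2 (Withdrawal of Patients From the Study):** "Patients must be withdrawn from the study for any one of the following reasons". Two reasons follow: loss to follow-up and withdrawal of consent.
- **Section 12.4:** hepatic, pulmonary and macular edema events stop study drug, and evaluation of the abnormality continues. It does not order withdrawal from the study.

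**The concern.** Section 9.4.4 separates stopping the drug from leaving the study. Section 9.5.6 merges the two for intolerance, in mandatory terms. Two sites could handle the same patient differently, each with a protocol sentence in support: one closes the patient out, the other keeps contact and records later relapses.

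This reaches the Part B analysis in two places. SAP Section 9.1.1 models confirmed relapses in the ITT population with log time on study as the offset, so both relapses and time depend on when the patient leaves the study. SAP Section 9.2.1 censors time to disability progression when follow-up ends, and study withdrawal is one of the named causes. Tolerability may differ between RPC1063 and interferon, so an exit caused by intolerance is related to treatment. Data not collected after such an exit cannot be recovered later.

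**Working it through.** **Step 1. Can the texts be reconciled?** Take a patient who stops because of an adverse event that he or she cannot tolerate.

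| Source | Drug | Study participation |
|---|---|---|
| 9.5.6 | stopped (implied) | must end |
| Synopsis; 9.1 Part B | stopped | continues, all efforts to follow |
| 9.4.4.1 | stopped | Early Termination and 4-week visits |
| 9.4.4.2 | not addressed | intolerance not listed as a reason to leave |
| 12.4 | stopped | evaluation of the abnormality continues |

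Reading *the study* in 9.5.6 as shorthand for study treatment would remove the conflict. Nothing in the protocol says so, and the two subsections of 9.4.4 use the terms for different events. No other section says which rule takes precedence.

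**Step 2. How many patients?** No document gives a rate of intolerance. All-cause dropout planned for Part B is 0.17 × 400 = 68 per arm (protocol 13.2) or about 0.12 × 400 = 48 per arm (SAP 5.1). Under those plans the rule reaches 0 to 68, or 0 to 48, patients per arm.

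**Step 3. Is stated power affected?** First reproduce the protocol's figure. Inputs from Section 13.2: rates 0.30 and 0.19, variance factor 1.3, 2 years of follow-up, two-sided alpha 0.025, 90% power.

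n per arm = 1.3 × (2.2414 + 1.2816)² × (1/(0.30 × 2) + 1/(0.19 × 2)) / [ln(0.30/0.19)]² = 1.3 × 12.411 × 4.298 / 0.2086 = 332.4, or 333 as stated.

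Now let all 68 planned dropouts contribute no time, which leaves 400 − 68 = 332 per arm, or 664 patient-years:

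- variance of the log rate ratio = 1.3 × (1/(664 × 0.30) + 1/(664 × 0.19)) = 0.01683, standard error 0.1297
- power = Φ(0.4568/0.1297 − 2.2414) = 0.900

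The planned 333 per arm (666 patient-years) gives 0.901 by the same formula. The sample size already assumes that dropouts contribute nothing, so the wording of 9.5.6 does not change it.

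**Step 4. Can a bias be signed?** In a simplified model, let p be the share of an arm's person-time that falls after stopping, and let a and b be its relapse rates on and off drug. With off-drug follow-up the arm's rate is a(1 − p) + bp; with follow-up cut at stopping it is a. The two differ by the factor 1 − p + p(b/a). The rate ratio between arms is unchanged only if this factor is the same in both arms. The documents give neither p nor b for any arm. Sections 9.1 and 9.4.4.1 allow other MS treatment after stopping, so b may lie above or below a. Neither size nor sign follows.

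**The case against.** The strongest reply is that the rewording may change little in practice. A patient who cannot tolerate the drug has stopped study medication, so 9.4.4.1 already calls for the Early Termination visit, which collects EDSS and MRI (Section 10.5), and the 4-week visit. These are the only visits scheduled after stopping, before or after the correction. Section 9.4.4.1 provides no continuing efficacy follow-up, and the follow-up in 12.4 is safety follow-up of the particular abnormality. One can add that 9.4.4.2 does not call its list complete.

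This limits the gain but does not remove it. The open-ended commitment in the synopsis and 9.1 is available only to a patient still in the study, and literal use of 9.5.6 removes it. Even if the list in 9.4.4.2 is not exhaustive, the conflict with the synopsis and 9.1 remains.

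A reader might also infer a second contradiction, on non-compliance. Section 9.5.9 (Part A) says that persistently non-compliant patients "should be discussed with the Medical Monitor to determine whether they should be withdrawn from the study", while 9.4.4.1 says "a patient may be discontinued from study medication for failure to comply with protocol requirements". Both statements are discretionary, so they do not contradict each other. The Part B sentence, "Compliance with RPC1063 capsules will be assessed as described above for Part A", carries over the assessment and not clearly its consequence.

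Nor does the point show a gap in SAP reporting of drug stops for adverse events: SAP Section 10.1.5 already tabulates and lists them.

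**Conclusion.** The conflict is real and no other section resolves it. Section 9.5.6 is mandatory, and followed literally it ends observation of ITT patients for a treatment-related reason that 9.4.4.2 does not list. It closes off the follow-up promised in the synopsis and 9.1, which can contribute to the relapse rate and to disability censoring.

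The point is modest in size. The ceiling of 68 (or 48) patients per arm assumes that actual dropout does not exceed the plan and that every dropout is due to intolerance; the true share is not given. Power stays at about 0.90.

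A reader might infer that the relapse-rate comparison is biased in favor of RPC1063, or that complete off-drug data to Month 24 are being lost. The documents support neither. The off-drug rates are unknown, and the protocol schedules no visits to Month 24 for patients who have stopped. What stands is an instruction that should be corrected so that sites act alike and the promised follow-up remains possible.

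**What to change.** Replace the sentence in Section 9.5.6 with, for example: *Patients unable to tolerate study drug must stop study medication (see Section 9.4.4.1) and be followed as described in Section 9.1 unless consent is withdrawn.* For Part A, the synopsis carries the same follow-up commitment.

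For consistency only, Section 9.5.9 (Part A) may also refer to stopping study medication in place of withdrawal from the study.

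The cost is one sentence, or two with the optional change. No visit, assessment, sample size or SAP analysis changes. Whether to schedule regular visits to Month 24 for patients who stop is a separate design choice for the sponsor and is not part of this request.
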